15.2 Primary Endpoint

The primary endpoint of this trial is complete cell cycle arrest. All eligible women who begin combination treatment and have an evaluable tumor Ki67 on Cycle 1 Day 15 will be included in the analyses of the primary study endpoint.

A patient with tumor Ki67 value $> 2.7\%$ on Cycle 1 Day 15 of combination treatment is considered to not have had a complete cell cycle arrest.

15.3 Trial Design

The expectation for complete cell cycle arrest, defined as $\leq 2.7\%$, at 2-4 weeks post neoadjuvant aromatase inhibitor alone, is 44% based on data from Z1031 Cohort B. Since PIK3CA mutation status does not affect neoadjuvant Ki67 response, the expected rate of complete cell cycle arrest for the PIK3CA mutant and wild type cohorts for single agent anastrozole is expected to be 44%.

The study is designed to ensure the sample size for the PIK3CA wild type cohort for the primary endpoint analysis. For the PIK3CA wild type cohort, thirty-three eligible patients will be enrolled. The sample size was chosen using Fleming's single-stage phase II design

to test the hypothesis that adding PD 0332991 would result in at least 50% improvement (44% versus 66%) in the complete cell cycle arrest rate, with 80% power and at 1-sided 0.05 significance level. If at least 20 patients in the cohort meet the criteria for complete cell cycle arrest, this regimen would be considered for future randomized trials.

Patients pre-registered to this trial and found to have PIK3CA mutation in the tumor are eligible to receive therapy in the PIK3CA mutant cohort. However, the enrollment to both cohorts will stop when 33 patients with PIK3CA wild type tumors have been enrolled and analyzed for the primary endpoint.

For the PIK3CA mutant cohort, depending on the frequency of mutation, 14 to 17 patients will be enrolled. The sample size for mutant cohort is determined primarily based on clinical feasibility rather than statistical power. However, according to the general guidelines regarding the sample size for translational studies[103], a sample size of 10-20 patients would provide reasonable precision for the estimation of pilot information regarding efficacy. If 10 complete cell-cycle arrest are observed out of 15 patients, for example, we will have 80% confidence that the “true” rate will fall between is ranged 47% and 83%.

For the endocrine resistant cohort, a Simon optimal two stage phase II clinical trial design will be used to assess whether the complete cell cycle arrest rate is at most 5% against the alternative that the complete cell cycle arrest rate is at least 20%. The study design proposed below yields a 90% chance of detecting a complete cell cycle arrest rate of at least 20% at an alpha level of 0.1.

Stage 1: Enroll 12 patients. If at least one complete cell cycle arrest is documented among these 12 patients, continue to Stage 2. Otherwise terminate enrollment for this patient cohort and declare that this regimen has insufficient anti-tumor activity in the neoadjuvant setting to recommend it for further testing in this patient population.

Stage 2: Enroll an additional 25 patients. If at most 3 complete cell cycle arrests are documented among the 37 total patients enrolled, this regimen will be considered to have insufficient anti-tumor activity in the neoadjuvant setting to recommend it for further testing in this patient population. Otherwise, this regimen may be recommended for further testing in the neoadjuvant setting for this patient population. For such a design, we will only have 7% chance to erroneously stop the trial at the 1st-stage if the true the complete cell cycle arrest rate is at least 20%. Conversely, there will be 54% chance to stop the trial at the 1st-stage if the true the complete cell cycle arrest rate is 5% or less.

Adverse events, the pace of accrual, other scientific discoveries, or changes in standard of care will be taken into account in any decision to terminate this trial earlier than designed.

A 90% confidence interval for the true complete cell cycle arrest rate will be calculated using the Duffy-Santner approach.

15.4 Sample Size and Trial Duration

We anticipate that 4-6 patients per month with clinical stage 2 or 3 estrogen receptor positive and HER2 negative invasive breast cancer will be screened for the *PIK3CA*. Approximately 40% of the patients have breast cancer with PIK3CA hotspot mutations. Thus, approximately 55 women with clinical stage 2 or 3 estrogen receptor positive and HER2 negative invasive breast cancer will be screened to enroll 33 evaluable patients to the PIK3CA wild type cohort.

The period encompassing enrollment, study treatment, and surgery will be about 20 months.

For the endocrine resistant cohort, we anticipate enrolling about one patient per month, completing Stage 1 in the approximately one year. If Stage 1 is successful, we will consider adding more sites to the study.

15.5 Data Analysis

All data analyses will be performed separately for each cohort unless otherwise specified.

Demographic and clinical characteristics of the sample, as well as response, toxicity by grade, and loss to follow-up will be summarized using descriptive statistics. The rate of complete cell cycle arrest will be calculated and the corresponding 90% confidence interval (CI) will be provided. The rates for pCR and PEPI 0 and their 90% CIs will also be calculated. The differences in overall survival (OS) and relapse-free survival (RFS) for patients with or without complete cell cycle arrest on C1D1 will be described using Kaplan-Meier product limit estimator and compared by log-rank tests. Similar analysis will be performed for complete cell cycle arrest on C1D15 or patients with or without PEPI 0, with the two cohorts combined or separately. A trajectory analysis (see below) will also be performed for this comparison.

Analysis of other secondary endpoints:

Clinical response rate: The clinical response rate will be estimated by the number of patients whose disease meets the WHO criteria of complete or partial response prior to surgery divided by the total number of eligible patients who began combination neoadjuvant treatment. A 90% confidence interval for the true clinical response rate will be calculated using the Duffy-Santner approach for the endocrine resistant cohort (2-stage design). The complete cell cycle arrest rates and the corresponding 90% confidence intervals will also be calculated for PIK3CA wild type and mutant cohorts separately and combined.

Radiological response rate: The radiological response rate will be estimated by the number of patients whose disease meets with WHO criteria for complete or partial response at the evaluation prior to surgery divided by the total number of eligible patients who began

combination neo-adjuvant therapy. A 90% confidence interval for the true radiographic response rate will be calculated using the Duffy-Santner approach. The analysis will be performed with the two cohorts separately and combined.

Adverse Events: All eligible patients that have initiated treatment will be considered evaluable for assessing adverse event rate(s). The maximum grade for each type of adverse event will be recorded for each patient using the NCI-CTCAE v4.0, and frequency tables will be reviewed to determine patterns. Additionally, the relationship of the adverse event(s) to the study treatment will be taken into consideration.

Ki67 suppression on Cycle 1 Day 1, Cycle 1 Day 15 and surgery: Following the approach of Dowsett et al. [26], the percent change in the Ki67 level from baseline will be determined on the log scale. A 95% t-confidence interval for the mean percent change in the Ki67 level from baseline will be constructed (if appropriate). The rate of complete cell cycle arrest on C1D1, C1D15, and surgery will be described by contingency tables compared by McNemar tests. Using trajectory analysis, we will also assess the association between distinct patterns of Ki67 change over time and clinical outcomes. Specifically, trajectory groups will be formulated to describe clusters of individuals with similar temporal patterns of Ki67 over time using finite mixture models with SAS procedure TRAJ. This method enables identification of the number of discrete trajectory types, and characterization of the shape and estimation of the prevalence of each type. We will choose the best models based on statistical tests (including Bayesian and Akaike information criterion, each of which test goodness-of-fit) and clinical judgment.

To assess the long term outcomes of patients treated in this trial: The long-term outcomes (i.e., pathologic complete response (pCr), local and distant recurrence, etc, as defined in section 12.4) will also be assessed in the PIK3CA wild and mutnt cohorts (separately and combined) and the endocrine resistant cohort, respectively. The categorical outcome will be summarized using contingency tables and compared by Fisher's exact test, while the time-to-event outcomes will be described using Kaplan-Meier product limit estimators and compared by log-rank test.

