1.9 Correlative Studies Background

1.9.1 Early Tumor Ki67 Assessment during Neoadjuvant Endocrine Therapy to Determine Treatment Response

In this trial, we plan to perform tumor biopsy to assess Ki67 following one month of endocrine therapy (pre-PD 0332991) and 2 weeks on combination of PD 0332991 and anastrozole (Cycle 1 Day 15). This is based on data from previous neoadjuvant endocrine trials which indicated that 2-4 week tumor Ki67 expression on neoadjuvant endocrine therapy is predictive of individual patient outcome long term[11, 25, 26]. In the IMPACT trial, 2-week Ki67 was a significant independent predictor of RFS (HR = 1.95; 95% CI = 1.23–3.07; $P = .004$) [25]. The 5-year RFS rates were 85%, 75%, and 60% for the lowest, middle, and highest values of 2-week Ki67 expression, respectively[25]. In the P024 trial, while baseline Ki67 was not associated with relapse, post 16-week treatment Ki67 levels had a robust association with RFS (HR = 1.4, CI = 1.2–1.6 per natural log unit increase; $P < .001$), and breast cancer-specific survival (HR = 1.4, CI = 1.1–1.7; $P = .009$) [11].

To further investigate these findings, Ellis et al examined the interaction between Ki67 levels and a PAM50-based definition of luminal A breast cancer versus luminal B breast cancer. By using ROC methodology, a cut point of Ki67 10% served as the best surrogate for the LumA versus LumB distinction [99]. The 10%

Ki67 cut point was then applied to the baseline and early on-treatment data in two data sets (Table 2), Preoperative Letrozole study (POL) [13] and IMPACT trial [25]. At baseline the dichotomized Ki67 definition was not significantly predictive for surgical Ki67 level, PEPI score or RFS in these modest sized sample sets. In contrast, high levels of Ki67 on the one month POL samples predicted a higher level of Ki67 in the surgical samples at four months after treatment initiation ($P=.01$), a poorer PEPI score ($P=0.01$), a smaller number of patients in the PEPI-0 group ($P=0.08$) and worse RFS ($P=0.003$). IMPACT data confirmed that a 2-week Ki67 $>10\%$ predicted higher Ki67 in the surgical specimen ($P=0.001$), a poorer PEPI score ($P=0.001$), smaller numbers of patients in the PEPI-0 group ($P= 0.004$) and worse RFS ($P=0.008$) (Table 2.3).

Table 2 Early Ki67 Assessments and Outcome in IMPACT and POL Trials		
POL 4W Ki67	% PEPI 0	RFS (events)
$>10\%$	1/19 (5%)	5/21 (23%)
$\leq 10\%$	10/36 (28%)	1/41 (2.4%)
P Value	$P=0.08$ (Fisher)	$P=0.003$ (log rank)

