1.9.6 Preoperative Endocrine Prognostic Index (PEPI)

In a multivariable analysis conducted on the P024 trial, three other post-neoadjuvant endocrine therapy tumor factors were determined to have independent prognostic value for relapse and death after relapse in addition to Ki67 [11]. These included pathological tumor size (T1/2 versus T3/4), pathological node status (positive or negative), the natural logarithm of the Ki67 value and the ER status of the tumor. A prognostic score, the preoperative endocrine prognostic index (PEPI),

was developed, which weighs each of these factors according to their associated hazard ratios. PEPI was then validated in an independent data set from the IMPACT trial [11]. No relapses were recorded in either trial in patients with T1, N0 tumors with a PEPI score of 0 (residual tumor with Ki67 index of 2.7% - natural logarithm of 1- or less with maintained ER expression) or in the rare patient with a pCR. PEPI has also recently been validated in the POL Trial (PreOperative Letrozole trial: A multicenter phase II trial of letrozole in postmenopausal women with clinical stage II or III hormone receptor positive breast cancer) [13]. In the combined analysis of P024 trial/POL trial, no relapse was observed with a median follow up of 61.3 months in the 24 patients in the PEPI 0 category. PEPI 0 as a prognostic marker on therapy therapy is being validated prospectively in the A011106 trial. An improvement in the rate of PEPI 0 following neoadjuvant PD 0332991 and anastrozole compared to the historical control would be of great interest for the design of adjuvant trials of PD 0332991.

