9.3.2 Tissue Processing and Ki67 Analysis

Upon receipt of the specimen, the 2 fixed biopsy specimens (A & B) at each time point will be further processed for tumor Ki67 analysis at the CLIA certified Anatomic and Molecular Pathology Core Labs at Barnes Jewish Hospital at St. Louis (CLIA number 26D2013203). After embedding in paraffin, one section from the tumor block will be stained with H&E to assess biopsy adequacy. Another section from the block will be incubated with antibody against Ki67 (clone 30-9) and then assayed using the Ventana Benchmark platform. The block and any remaining sections will be returned to the Tissue Procurement Core Facility at the completion of testing. Both cores will be reviewed and will be taken into account for the scoring. Ki67 scoring is reported as a quantitative/continuously distributed value.

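### Section 15.5 relates OS and RFS to Ki67 only through groups; no survival model uses ln Ki67 as a continuous value, and the cost is largest in the endocrine-resistant cohort

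*Combined protocol and SAP*

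**What the plan says.** Section 15.5 sets out the survival comparisons. OS and RFS for "patients with or without complete cell cycle arrest on C1D1 will be described using Kaplan-Meier product limit estimator and compared by log-rank tests". The text then carries the same method to the later time point and to PEPI: "compared by log-rank tests. Similar analysis will be performed for complete cell cycle arrest on C1D15 or patients with or without PEPI 0". The sentence after that adds: "A trajectory analysis (see below) will also be performed for this comparison". Later in 15.5 the trajectory analysis is described as finite mixture modelling in SAS PROC TRAJ. It sorts women into discrete types by their Ki67 course and relates those types to outcome. Section 15 contains no Cox model or other survival regression, and gives no alpha, event count or power for any survival comparison.

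The measurement itself is not grouped. Section 9.3.2 states: "Ki67 scoring is reported as a quantitative/continuously distributed value". The background in 1.9.1 gives the P024 association with RFS as a hazard ratio of 1.4 "per natural log unit increase". For IMPACT it says: "The 5-year RFS rates were 85%, 75%, and 60% for the lowest, middle, and highest values of 2-week Ki67 expression". Section 1.9.6 lists, among the factors behind PEPI, "the natural logarithm of the Ki67 value and the ER status of the tumor".

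**The concern.** Long-term outcome is secondary objective 10, and these are the analyses that link it to Ki67. Cutting a continuous predictor at 2.7% treats every woman on one side of the cut as alike. The loss is modest when the cut falls near the middle of the distribution and severe when it leaves a small low-risk group, because a group of about seven women who are expected to do well contributes almost no events.

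The endocrine-resistant cohort, the one still open for neoadjuvant treatment, is designed around that situation: the arrest rate is 5% under its null and 20% under its alternative. A non-significant log-rank result there would be close to certain even if on-treatment Ki67 predicted relapse as strongly as the cited trials suggest. The trajectory analysis does not fill the gap, since it too forms groups and gives no effect per unit of Ki67.

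**Working it through.** **The plan's own design figures.** For the endocrine-resistant cohort (15.3), the rule of 0/12 then 3/37 gives alpha 0.093, power 0.902, and early stopping of 54.0% at a 5% arrest rate and 6.9% at 20%. The stated figures reproduce. They concern the arrest rate; nothing comparable is stated for survival.

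**Inputs from the documents.**
- n = 37. Arrested: 37 × 0.05 = 1.9 to 37 × 0.20 = 7.4, so about 7 v 30 at the alternative (15.3).
- Events: in Table 2 (1.9.1), women with Ki67 above 10% had 9/35 and 5/21 RFS events, so 37 × 9/35 = 9.5 and 37 × 5/21 = 8.8.
- Closed cohorts: 39 of 45 arrested at C1D15, wild type 22 of 28 (1.8); expected C1D1 arrest 44% (15.3). Section 1.8 says 26 women were arrested at C1D15 but not at C1D1. If all 45 had a C1D1 value, C1D1 arrest was between 39 − 26 = 13 (29%) and 13 + 6 = 19 (42%), so one third is also shown.

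**Assumptions not in the documents.** Normal ln Ki67; log hazard linear in ln Ki67; two-sided 5% tests; administrative censoring at 5 years with no other loss. Two gradients are used:
- IMPACT, reading the three bands as tertiles: slope = ln[ln(0.60)/ln(0.85)] / 2.18 = 0.525 per SD, a hazard ratio of 1.69 per SD, with 5-year RFS 73%.
- P024: hazard ratio 1.4 per ln unit, SD 1.0 to 1.5, with 5-year RFS 75%.

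**Simulated rejection rates for RFS, log-rank v Cox score test on ln Ki67.**

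| Split | IMPACT gradient | HR 1.4 per ln unit, SD 1.0–1.5 |
|---|---|---|
| Endocrine-resistant, 7 v 30 | 3–4% v 36% | 2% v 17–32% |
| C1D1, n = 45, 44% arrested | 25–26% v 41–43% | 12–22% v 19–38% |
| C1D1, n = 45, one third arrested | 19–20% v 43% | 10–16% v 20–38% |
| C1D15, 39 v 6 | 33% v 42% | 18–30% v 20–38% |

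For wild type alone (22 v 6) the gain is about 0 to 3 points. With no association, the 7 v 30 log-rank test rejects about 4% of the time, so under the cited gradients it does no better than under the null.

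**Why 7 v 30 fails.** Suppose none of the 7 relapses and 10 of the 30 do. Summing over the 10 event times with 37, 36, …, 28 at risk, the expected events in the arrested group are Σ 7/r = 2.17 and the variance is 1.70. Then z = 2.17/√1.70 = 1.67 and p = 0.10. With 12 events p = 0.06; 13 are needed for p < 0.05. At the expected event count, perfect separation is not significant.

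**How far the Cox term helps.** With 9 events, power = Φ(√9 × SD × ln 1.4 − 1.96). This is Φ(1.01 − 1.96) = 17% at SD 1.0 and Φ(1.51 − 1.96) = 33% at SD 1.5, in line with the simulation. For 80% power the events needed are (1.96 + 0.84)² / (SD × ln 1.4)², about 69 at SD 1.0 and 31 at SD 1.5.

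**C1D1 in the endocrine-resistant cohort.** Entry requires Ki67 above 10% on endocrine therapy (3.4.1), and an entry research biopsy can stand in for the C1D1 one (10.2, footnote W). The C1D1 arrest split there is empty or nearly so.

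**The case against.** Five points deserve weight.

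1. A reader might infer that the log-rank tests are the only link between Ki67 and survival. The documents do not support that: the trajectory analysis is attached to the same comparison. What stands is that it also works through groups.

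2. A reader might infer that the cut is what defeats the survival analysis. Events are the main limit. About 9 to 10 are expected and 31 to 69 would be needed, so the Cox model does not make the question answerable. If the cohort stops at 12 women, neither approach works.

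3. The cited evidence is not purely a gradient. Section 1.9.1 also uses a 10% cut, and 1.9.6 rests on PEPI 0, which contains the 2.7% cut. Arrest at 2.7% is the primary endpoint, so comparing survival by it is a legitimate planned question. The PEPI 0 rate is a named secondary objective, and nothing computed here supports replacing PEPI 0 with an ordinal score.

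4. Later treatment depends on Ki67. Above 10% at C1D15, study drug stops and surgery or chemotherapy is recommended (9.3.1, 5.7). Access to adjuvant PD 0332991 depends on the 10% and 2.7% thresholds (3.5.1, 5.3). The hazard ratio therefore mixes prognosis with treatment, and log-linearity is doubtful. If the top 40% of women are assumed to switch with a treatment hazard ratio of 0.7 or 0.5, Cox power at 7 v 30 falls from 36% to about 20% or 10%. Log-rank power is then about 1 to 2%, so the ordering holds.

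5. The gradients are borrowed from endocrine therapy without a Cdk4/6 inhibitor, and the P024 figure is for Ki67 after 16 weeks. The contrast also shrinks if arrest is more common: with about half arrested, the IMPACT gradient gives about 23% v 36%. The C1D15 sentence speaks of the two cohorts; applying it to the endocrine-resistant cohort relies on the default in 15.5 that analyses are done for each cohort separately.

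**Conclusion.** The gap is real and cheap to close. Every planned link between Ki67 and survival goes through groups, while the measurement and part of the cited evidence are on a continuous log scale. In the endocrine-resistant cohort at its 20% alternative, the arrest-based log-rank test rejects in about 2 to 4% of simulated trials, against about 17 to 36% for a Cox term on ln Ki67. The gain is moderate for C1D1 in the closed cohorts (about 25% v 41 to 43% at 44% arrested under the IMPACT gradient) and small for C1D15, both 39 v 6 and wild type alone.

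These figures rest on normal ln Ki67, the assumed SD, a log-linear hazard and gradients taken from other trials. They are for RFS; OS was not simulated. Power stays below 50% in every case, so the benefit is an effect estimate with an honest interval in place of a yes/no test that can hardly reject. A null result would remain weak evidence under either method.

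**What to change.** In 15.5:
- Add a Cox model with continuous ln Ki67, at C1D1 and at C1D15, as the test of the Ki67–outcome association. Set zero values to the assay's smallest reportable value. Report the hazard ratio per ln unit with its CI.
- Keep the planned Kaplan–Meier curves and log-rank comparisons by arrest and by PEPI 0, and leave PEPI 0 as it is.
- Label all survival comparisons exploratory.
- State that the hazard ratio combines prognosis with Ki67-driven later treatment, citing the C1D15 rule above 10% and the Ki67 conditions for adjuvant PD 0332991.
- Accompany each model with a check of linearity. With this few events it will show only gross departures.

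The cost is a paragraph of SAP text and one model per time point on values already collected. The downside is the log-linearity assumption, which the treatment rules may break.

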2.2 Secondary Objectives

1. To determine the rate of complete cell cycle arrest, defined by Ki67 $\leq 2.7\%$, following 2 weeks (C1D15) of neoadjuvant PD 0332991 in combination with anastrozole in women with clinical stage II or III ER+/HER2- breast cancer with PIK3CA hot spot mutation.
2. To determine the rate of complete cell cycle arrest, defined by Ki67 $\leq 2.7\%$, following 2 weeks (C1D15) of neoadjuvant PD 0332991 in combination with anastrozole in women with clinical stage II or III ER+/HER2- endocrine-resistant breast cancer.

The following objectives will be assessed in PIK3CA mutant cohort and in PIK3CA Wild Type (WT) cohort combined or separately, and assessed separately in the endocrine resistant cohort.

3. To compare the rate of complete cell cycle arrest between C1D1 and C1D15

4. To assess Ki67 level on serially collected tumor specimens (baseline, C1D1, C1D15, and surgery)
5. To determine the rate of PEPI 0 score with the study drug therapy
6. To determine the pathologic complete response (pCR) rate of study drug therapy
7. To assess the rate of clinical response and radiologic response in the neoadjuvant setting
8. To determine the safety profile (on therapy and post 30 days of therapy completion) of the study therapy during 4 months of neoadjuvant therapy.
9. To determine the safety profile of the study therapy during 2 years of adjuvant therapy.
10. To assess the long term outcomes of patients treated in this trial.

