5.7 Treatment/Follow-up Decision Tree

Any patient who registers on study and then withdraws her consent prior to receiving any PD 0332991 will be considered a cancellation. No further follow-up is required. Future treatment is at the discretion of their treating physician.

If a patient is found not to have fulfilled all the eligibility requirements after starting PD 0332991, she will be removed from study treatment. All study forms up to the point of study treatment discontinuation are to be submitted. These patients will be observed for

AEs for 30 days following the last dose of PD 0332991 or the resolution of AEs at least possibly related to PD 0332991, whichever comes later. Future treatment is at the discretion of the treating physician. No further follow-up is required.

All patients except for those who withdrew consent for follow up or who refused to undergo surgery will be followed for 30 days after surgery, then yearly to document recurrence and survival status for 5 years or until recurrence whichever comes first (see Section 10.3).

Patients who received adjuvant PD 0332991 will be followed as described in Section 10.3 during adjuvant PD 0332991 therapy, then yearly following completion of PD 0332991 to complete a total of 5 years of follow-up post surgery. Should a patient discontinue adjuvant PD 0332991 early, she would be followed annually following the completion of PD 0332991 to get as close as possible to 5 years of post-surgery follow-up.

If protocol therapy was discontinued due to Ki67 > 10% on C1D15 or estradiol level in the premenopausal range in patients on goserelin, or discontinued PD 0332991 prior to completion of planned duration of therapy, the patient will be observed for AEs for 30 days following the last dose of PD 0332991 or the resolution of AEs at least possibly related to PD 0332991, then yearly to complete 5 years of follow up after surgery or until recurrence (whichever comes first). Neoadjuvant chemotherapy per physician choice is recommended before surgery. Pathologic response will be documented.

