7.7 Reporting to Pfizer

Within 24 hours of first awareness of the event (immediately if the event is fatal or life-threatening), the PI or designee will report to Pfizer by facsimile any serious adverse drug experience (as defined in Section 7.9) that occurs during the SAE reporting period (as defined in Section 7.11) in a study subject assigned to receive PD 0332991. Such SAEs will be reported using MedWatch form and the Pfizer Reportable Event Fax Cover Sheet (Appendix G) should also be included. SAEs should be reported as soon as they are determined to meet the definition, even if complete information is not yet available.

Even though there may not be an associated SAE, exposure to PD 0332991 during pregnancy or lactation is reportable.

Secondary sites must submit a completed MedWatch form to the Washington University PI and research coordinator within the specified time frame. The Washington University PI will be responsible for submitting all MedWatch forms from secondary sites to Pfizer.

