13.0 DATA AND SAFETY MONITORING

In compliance with the Washington University Institutional Data and Safety Monitoring Plan, the Data and Safety Monitoring Committee (DSMC) will meet to review toxicity data at least every 6 months following the activation of the first secondary site. The report will be prepared by the statistician with assistance from the study team and will be submitted to the Quality Assurance and Safety Monitoring Committee (QASMC). This report will include:

- HRPO protocol number, protocol title, Principal Investigator name, data coordinator name, regulatory coordinator name, and statistician
- Date of initial HRPO approval, date of most recent consent HRPO approval/revision, date of HRPO expiration, date of most recent QA audit, study status, and phase of study

- History of study including summary of substantive amendments; summary of accrual suspensions including start/stop dates and reason; and summary of protocol exceptions, error, or breach of confidentiality including start/stop dates and reason
- Study-wide target accrual and study-wide actual accrual including numbers from participating sites
- Protocol activation date at each participating site
- Average rate of accrual observed in year 1, year 2, and subsequent years at each participating site
- Expected accrual end date and accrual by site.
- Objectives of protocol with supporting data and list the number of participants who have met each objective
- Measures of efficacy
- Early stopping rules with supporting data and list the number of participants who have met the early stopping rules
- Summary of toxicities at all participating sites
- Abstract submissions/publications
- Summary of any recent literature that may affect the safety or ethics of the study

Until such a time as the first secondary site activates this protocol, a semi-annual DSM report to be prepared by the study team will be submitted to the QASM Committee beginning 6 months after study activation at Washington University.

The study principal investigator and Research Patient Coordinator will monitor for serious toxicities on an ongoing basis. Once the principal investigator or Research Patient Coordinator becomes aware of an adverse event, the AE will be reported to the HRPO and QASMC according to institutional guidelines.

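### The planned adverse event rates cover only eligible treated women, so toxicity in a woman found ineligible after starting PD 0332991 is missing from the safety tables

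*Combined protocol and SAP*

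**What the plan says.** Under Adverse Events, Section 15.5 names the women who count: "All eligible patients that have initiated treatment will be considered evaluable for assessing adverse event rate(s". For each of them the maximum grade of each event type is recorded, and frequency tables are then reviewed. Earlier in Section 15.5 a general sentence says that "toxicity by grade, and loss to follow-up will be summarized using descriptive statistics", and it describes the population only as the sample.

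Section 5.7 deals with late-discovered ineligibility: "If a patient is found not to have fulfilled all the eligibility requirements after starting PD 0332991, she will be removed from study treatment". Two duties follow. On data, "All study forms up to the point of study treatment discontinuation are to be submitted". On safety, the follow-up is to cover "AEs for 30 days following the last dose of PD 0332991 or the resolution of AEs at least possibly related to PD 0332991", taking the later of the two.

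Safety is a secondary objective. Section 2.2 lists it for the neoadjuvant phase, "To determine the safety profile (on therapy and post 30 days of therapy completion) of the study therapy during 4 months of neoadjuvant therapy", and again for the two years of adjuvant therapy.

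Two other safety channels carry no eligibility limit. The monitoring report in Section 13.0 contains a "Summary of toxicities at all participating sites". Section 7.7 requires serious events to be reported to the drug supplier when they occur "in a study subject assigned to receive PD 0332991".

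**The concern.** Restricting an analysis to eligible patients has a rationale for efficacy, and Sections 15.2 and 15.5 apply the same restriction to cell cycle arrest and to response. For safety, the question is what happened to women who were exposed to the drug, and a later finding of ineligibility does not undo exposure.

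The exclusion may also be related to the outcome. Several eligibility criteria in Section 3 exist for safety reasons: marrow and organ function, QTc, strong CYP3A4 inhibitors or inducers, and antiretroviral therapy, for which the protocol itself cites pharmacokinetic interaction and infection risk. A woman treated despite breaching one of these may be more prone to toxicity than the rest.

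At stake is the completeness of the safety tables for a stated objective. The cohorts are small enough for one or two women to decide whether a rare severe event appears at all.

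**Working it through.** The documents give no figure that depends on this population, so there is none to reproduce. The check has two parts.

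**Reading the sections together**

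1. Section 5.7 shows that the group of treated but ineligible women is foreseen and that its adverse event data are collected.
2. The Adverse Events paragraph of Section 15.5 requires both eligibility and initiated treatment. A woman in that group meets only the second condition.
3. Sections 12, 13 and 15 define no all-treated safety set. The general toxicity sentence in Section 15.5 names no population that would clearly bring her back.
4. She is therefore absent from the planned adverse event rates, although present in the database, in serious event reporting and in the monitoring summaries.

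**Size**

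Inputs: N = 37, the full size of the endocrine resistant cohort (Section 15.3), used because Section 15.5 analyses cohorts separately by default. The number of treated but ineligible women, k, is not given; k = 1 to 5 is an assumption. The event counts are also assumptions.

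Formulas, with x women having the event, y of whom are ineligible:

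- all treated: x / N
- eligible only: (x − y) / (N − k)

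Intervals are Clopper-Pearson 95%, two-sided. For zero events in n women the upper limit is 1 − 0.025^(1/n).

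| Assumed situation | All treated | Eligible only |
|---|---|---|
| x = 1, k = 1, y = 1 | 1/37 = 2.7% | 0/36 = 0% |
| x = 2, k = 2, y = 2 (worst case) | 2/37 = 5.4% (0.7-18.2%) | 0/35 = 0% (upper limit 1 − 0.025^(1/35) = 10.0%) |
| x = 3, k = 1, y = 1 | 3/37 = 8.1% | 2/36 = 5.6% |
| x = 3, k = 2, y = 2 | 3/37 = 8.1% | 1/35 = 2.9% |
| x = 3, k = 1, y = 0 | 3/37 = 8.1% | 3/36 = 8.3% |
| x = 3, k = 5, y = 0 | 3/37 = 8.1% | 3/32 = 9.4% |

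The rows with y = 0 matter for direction. If the excluded women have no events, the eligible-only rate rises. The restriction lowers the rate only when the event is more frequent among the excluded women than among the others.

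**The case against.** Five arguments can be made against the point.

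- **The events are not lost.** Forms and follow-up are required, and serious event reporting and the monitoring summaries are not limited to eligible women. Section 15.3 also lets adverse events inform early termination without such a limit. This stands. A reader might infer that the plan discards these data or hides them from oversight, and the documents do not support that. What is missing is their place in the planned rates.
- **The general toxicity sentence might include these women.** It is silent on eligibility, so it is too strong to say that every toxicity summary excludes them. But it does not define a population either, and the specific sentence on adverse event rates does.
- **The direction of bias is not established.** This stands. A reader might infer that the rates are necessarily too low. Ineligible women come off treatment when identified, so their exposure is shortened and they may have fewer events. Many ways of being ineligible, such as stage, receptor status, Ki67 or a previous excisional biopsy, have no evident link to drug toxicity.
- **The group is probably small.** Section 4.2 has the coordinating centre confirm eligibility, from a signed checklist and source documents, before registration. This stands, and it limits the expected size.
- **No decision rule uses this denominator.** Also true: the adverse event output is descriptive. It is nevertheless the planned analysis for a stated objective.

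**Conclusion.** The point holds as a defect in the definition of the safety population. Followed literally, Section 15.5 leaves exposed women out of the adverse event rates, although Section 5.7 expects such women and collects their data. The effect can be bias in either direction. Downward is plausible where the breached criterion concerns organ function, QTc or interacting drugs, but the documents do not establish it.

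The size depends on a number the documents do not give. With one or two such women in a cohort of 37, common toxicities would move little, whereas a rare severe event could disappear from the table. The case in which both of two excluded women have the event and no other woman does is a worst case, not an expectation. The change is worth making because the repair is simple and the data already exist. It does not call the trial's safety oversight into question.

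**What to change.** Reword the sentence in Section 15.5 along these lines: *All patients who received at least one dose of PD 0332991, regardless of eligibility, are included in the adverse event analysis.* An eligible-only table may be kept as supportive.

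The new wording also settles what initiating treatment means. In the PIK3CA cohorts it could now be read as starting Cycle 0 anastrozole. Section 5.7 already uses receipt of PD 0332991 as a dividing line, since a woman who withdraws consent before any dose is a cancellation.

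The cost is one sentence. No new data are needed, and no treatment or follow-up rule changes. The downside is that the reported rates may look slightly less favourable.
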